#### 9. Outcome Measures

Assessments will take place at baseline, and at 4, 16, 34, and 52 weeks post-release. Baseline assessments (including informed consent, locator, and release of information paperwork) will take place in person at the jail; RAs will offer to read each study assessment aloud. Follow-up assessments will take place by telephone (the most feasible way to do follow-ups with this population), unless a participant is reincarcerated, in which case the follow-up assessment will take place in person at the jail/prison. If a participant is in a residential treatment facility, the follow-up assessment may take place by phone or in person at the residential treatment facility.

Table C1: Assessments	Туре	Time (min)	Baseline	4, 16, 34, and 52 week Follow-up
Suicidal Ideation and Behavior				
Columbia Suicide Severity Rating Scale (C-SSRS) 181	Interview	20	X	X
L.I.F.E. 182 – suicidal ideation and behavior	Interview	10		X
Suicide deaths: record review (state/national death registry)	Objective	0		X
Hospitalizations: Tx History Interview, record review (local hospitals)	Objective	0	X	X
Psychiatric Symptoms:				
DSM-5 Cross-Cutting Measure	Self-Report	7	X	X
K6	Self-Report	1	X	X
LEC/PCL	Self-Report	7	X	X
AUDIT and DUDIT	Self-report	7	X	X
Overdose	Self-report	10	X	X
Functioning: VR-12  from RAND Medical Outcomes Study	Self-Report	3	X	X
Hypothesized Mechanisms				
Treatment utilization: Treatment History Interview 	Interview	8	X	X
Belongingness: Interpersonal Needs Questionnaire-12 	Self-Report	5	X	16 ,34, 52 only
Suicide-related problem-solving: Suicide Related Coping Measure	Self-Report	5	X	16, 34, 52 only
Diagnosis: Mini International Neuropsychiatric Interview (MINI)  : lifetime psychosis, mania/hypomania, major depressive episode	Interview	10		4 week only
Safety Plan use in the context of Substance Abuse	Interview	10		52 only
Total patient time for interview (min)			Consent[contact]

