Hypothesized mechanisms of SPI effects. We define treatment utilization (primary) as the number of outpatient mental health and substance use visits attended in the community in the 3 months prior to baseline or since the last assessment, as indexed by the THI. Belongingness (exploratory) will be assessed using the Interpersonal Needs Questionnaire (INQ-12). 185,193 Suicide-related problem-solving (exploratory) will be assessed using a standard checklist of suicide safety behaviors and asking whether each was utilized during the most suicidal period since the last interview (identified on the C-SSRS). The checklist includes two subscales to minimize assessment reactivity: the sum of the number of recommended (e.g., call a friend) and the sum of the number of not recommended (e.g., use drugs) responses to suicidal thoughts or urges. These are the most direct, objective measures possible given the time-pressed, chaotic jail setting for baseline assessments and telephone follow-up.

Additional outcomes. Suicide deaths. Given the low incidence of suicide deaths, even in this high risk sample, we do not expect to have sufficient numbers of suicide deaths (separate from the suicide event composite) for meaningful analyses. However, we will track number of suicide deaths using all possible data sources, including hospital records and reviews of state and national death registries. Although our intervention does not target re-arrest directly, it is possible that by increasing service linkage, SPI could reduce re-arrest; therefore, we will assess number of re-arrests and compare conditions on this variable. We will also track days incarcerated in the year after the index release to weight participants by time in the community for other analyses. In addition, a brief questionnaire was added to the end of the study to collect open-ended participant feedback about his/her experience in the study.

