**Missing Data.** We will collect medical record and death record data on all participants. Self-reported count (e.g., suicide events) and historical (e.g., weekly LIFE ratings) data from missed assessments will be gathered at later follow-up assessments. We will use multiple imputation to deal with missing data. We will compare treatment conditions on rates of missingness and time to missingness and will test whether baseline characteristics are associated with missingness. Finally, we will perform a sensitivity analysis in which we impute extreme values for missing data to determine the sensitivity of analysis results to missing data.

**Outcomes.** Primary. We will test the hypothesis that, relative to SOC alone, SPI + SOC will result in fewer suicide events over the 52 week follow-up period, using ordinal logistic regression with lifetime suicide attempts events at baseline as a covariate. The analysis framework will be multivariate ordinal dependent variable regression. We begin with ordinal models because our simulations suggest the count outcome will not likely exceed 3. We will explore using different models such as zero-inflated Poisson or zero-inflated negative binomial with an offset defined by the length of follow-up and time in the community (as opposed to reincarcerated), and other reasonable approaches. Determination of the appropriate modeling will be determined using model selection (information) criteria and the determination will be made blind to the effect of the SIP intervention. Secondary. We will separately test the hypotheses that, relative to SOC alone, SPI + SOC will result in fewer suicide attempts, fewer weeks of active suicide ideation (per the LIFE calendar), lower severity of suicide ideation (C-

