**Mechanisms of intervention effects.** We will separately test the hypotheses that, relative to SOC alone, SPI + SOC will result in more treatment utilization (number of outpatient mental health and substance use visits as assessed by the THI), more sense of belongingness (INQ-12 Belongingness Scale score), and better suicide-related problem solving (as assessed by the safety behavior checklist), our proposed primary and exploratory mechanisms, using Mplus, which can accommodate both standard and Poisson-class regression methods. We will then test the hypothesis that treatment utilization, suicide-related problem-solving skills, and belongingness (1) predict suicide events, and (2) mediate the effects of SPI on suicide events in a structural equation model framework to decompose total effects into direct and specific indirect effects. As recommended by MacKinnon et al, the statistical significance of the indirect effect will be assessed using bias-corrected bootstrapped standard errors; 95% CI estimates will be provided.

**Predictors/Personalization**. We will explore gender, race/ethnicity, lifetime suicide attempts, lifetime highest C-SSRS SI intensity score, severe mental illness (schizophrenia, bipolar disorder), substance use, and # of lifetime arrests as moderators. We expect that SPI is appropriate for a full range of at-risk jail detainees.

Cost-effectiveness analyses. We propose a comparative cost effectiveness (CE) analysis of SPI + SOC relative to SOC. The primary effectiveness measure is the sum of suicide-related hospitalizations and medically treated and fatal suicide acts, with a secondary measure of QALYs (see D2.12). Following widely accepted CE analysis guidelines, analyses will adopt a societal perspective, considering all economic costs regardless of source. If direct cost savings exceed the program costs, the program is said to offer net cost savings. We describe our statistical plan for determining mean change in and standard deviations of these measures above. The CE ratio equals  $\Delta C/\Delta E$ , where  $\Delta C$  is the difference in costs between SPI + SOC and SOC alone and  $\Delta E$  is the difference in the outcome measure. Using the Crystal Ball add-in to Excel, we will bootstrap 95% confidence intervals around the CE ratio and calculate a cost-effectiveness acceptability curve. Sensitivity analysis will examine CE ratios at 0%, 1% and 5% discount rates.

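### The exploratory problem-solving mediator has no meaningful value for a participant with no suicidal period, and SPI is expected to change who has one.

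*Combined protocol and SAP*

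**What the plan says.** Section 9 (Hypothesized mechanisms of SPI effects) introduces the measure: "Suicide-related problem-solving (exploratory) will be assessed using a standard checklist of suicide safety behaviors". The score comes from "asking whether each was utilized during the most suicidal period since the last interview", with that period identified on the C-SSRS. There are two counts. One is the number of recommended responses. The other is "the sum of the number of not recommended (e.g., use drugs) responses to suicidal thoughts or urges".

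Section 10A (Mechanisms of intervention effects) gives the checklist two jobs. It is an outcome, on which SPI should produce "better suicide-related problem solving (as assessed by the safety behavior checklist"). It is also one of three mediators expected to "1) predict suicide events, and (2) mediate the effects of SPI on suicide events in a structural equation model framework".

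The secondary hypotheses in Section 10A expect SPI to give "fewer weeks of active suicide ideation (per the LIFE calendar), lower severity of suicide ideation".

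Table C1 has a single row for the construct, "Suicide-related problem-solving: Suicide Related Coping Measure". It is a self-report of 5 minutes at baseline and at weeks 16, 34 and 52, and is not collected at week 4. The table gives no items, scoring or recall window.

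Neither section says how to score an interval without a suicidal period. The only relevant text is the general missing-data paragraph in 10A: multiple imputation, a comparison of missingness by arm, and a sensitivity analysis with extreme values.

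**The concern.** The score exists only if the person was suicidal during the interval. That is a post-randomization state which the intervention is meant to make rarer, so the two arms will not contribute scores on the same footing.

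An analyst has three defaults, and each one fails.

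- **Score zero.** On the recommended subscale, a person who stayed well looks like a person who coped badly. On the not-recommended subscale, the same person looks like someone who coped well. The biases run in opposite directions.
- **Drop.** The arms are compared within subgroups that treatment helped to select. Randomization no longer protects the comparison, and the sample shrinks.
- **Impute.** Multiple imputation supplies behavior for a crisis that did not happen. The value is not missing; it does not exist. Extreme-value imputation has the same difficulty.

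The mediation path is the most exposed. People who have suicide events will usually have had a suicidal period, so they can score above zero, while people who stayed well cannot. At stake is a wrong statement about how SPI works, not about whether it works. Baseline is little affected, because entry requires ideation with intent or an attempt in the past month.

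**Working it through.** **1. The plan's own mediation figure.** Section 10B gives a detectable mediation effect of 0.11 to 0.13 as the intervention-mediator correlation ρ goes from 0.2 to 0.5. In standardized linear form, with two-sided α = 0.05 and 80% power, b = (1.960 + 0.842)/√(n(1 − ρ²)).

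- n = 624 (78% of 800): 2.802/√599.0 = 0.1145 and 2.802/√468 = 0.1295. This matches the plan.
- n = 800: 0.101 and 0.114. This does not match.

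The stated figure therefore takes all 624 evaluable people as having a score. That base is already too large for this measure: 624 counts anyone with at least one follow-up, including week 4. Taking 92% of 800 = 736 released, the plan's follow-up rates give 736 × 0.80 = 589, 736 × 0.75 = 552 and 736 × 0.70 = 515 at weeks 16, 34 and 52.

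**2. Dropping people without a period.** The documents do not give the share with a suicidal period, so it is an assumption, shown as a range. The same formula applies to the plan's base of 624. Power at the plan's own detectable effect is Φ(2.802√f − 1.960), where f is the share with a period.

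| f | n | Detectable b (ρ = 0.2 to 0.5) | Power at the stated effect |
|---|---|---|---|
| 100% | 624 | 0.11 to 0.13 | 80% |
| 80% | 499 | 0.13 to 0.14 | 71% |
| 60% | 374 | 0.15 to 0.17 | 58% |
| 40% | 250 | 0.18 to 0.20 | 43% |

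Using the smaller wave-specific bases would make each row slightly worse.

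**3. Scoring zero, between-arm test.** Let p be the share with a period and m the mean number of responses within a period (0 = SOC, 1 = SPI). The zero-scored arm mean is p × m. On the recommended subscale SPI looks better only if m₁/m₀ > p₀/p₁.

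| p₀ vs p₁ (assumed) | p₀/p₁ | Gain needed to break even |
|---|---|---|
| 80% vs 70% | 1.143 | 14% |
| 50% vs 40% | 1.250 | 25% |
| 40% vs 30% | 1.333 | 33% |

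On the not-recommended subscale, suppose behavior within a period is identical in the arms. At 50% vs 40% the SPI mean is still 0.40/0.50 = 80% of the SOC mean, an apparent 20% improvement with no change in coping.

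**4. How the sign varies.** Assume a latent severity shift of d = 0.28 and an SOC mean of 2 recommended responses within a period. The expected zero-scored difference is p₁m₁ − p₀m₀.

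- 50% vs 39%, 25% gain: 0.39 × 2.5 − 0.50 × 2 ≈ −0.02. The within-period difference is about +0.5, so the effect is hidden.
- 31% vs 22%, 25% gain: 0.219 × 2.5 − 0.308 × 2 ≈ −0.07, reversed.
- 69% vs 59%, 25% gain: 0.588 × 2.5 − 0.692 × 2 ≈ +0.09, attenuated.
- 50% vs 39%, 50% gain: simulated +0.18 against about +1.0 within a period, attenuated but positive.

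**5. Scoring zero, mediator-event slope.** In simulations under these assumptions, with coping truly lowering events, the slope of events on the mediator for 50% vs 39% and a 25% gain was −0.16 among people with a period and +0.08 with zeros included. With a 50% gain it was +0.07 with zeros included. For 69% vs 59% and a 25% gain it was +0.03.

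The reason can be written down. Within one arm, suppose people without a period have no events, and those with a period average e events. The zero-scored covariance is then p × (within-period covariance) + p(1 − p) × m × e. The second term is positive however well coping works.

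**The case against.** The strongest reply is that this mediator is exploratory, that treatment utilization is the primary mechanism, and that asking what someone did at their worst moment is deliberate: SPI teaches behavior for crises, and the checklist records enacted behavior. All of that is right, and it limits the weight of the point. It does not supply a value for people who had no crisis, and Section 10A still plans a between-arm test and indirect effects with 95% confidence intervals.

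A second reply is that the missing-data paragraph already covers the gap. It covers values that exist but were not collected. It does not fit a value that is undefined.

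A third reply concerns the size, and it stands: every share and gain above is assumed. A reader might infer that the checklist will hide or reverse SPI's effect. The documents do not support that. The sign depends on m₁/m₀ against p₀/p₁, and a large enough within-period gain leaves a positive, attenuated effect. Nor is the bias only against SPI, because the not-recommended count moves the other way.

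A reader might also infer that Table C1 schedules a different instrument that every participant can complete, ready to be substituted. That is not shown. There is one row, one name and no item content, so it may be the same checklist under another label, and nothing says it can be answered without a suicidal period.

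**Conclusion.** The point holds for one exploratory mechanism and is worth correcting. As defined, the checklist cannot give an interpretable between-arm contrast or indirect effect in the whole sample, because having a score depends on a post-randomization state that SPI is expected to change. This rests on the definition in Section 9, the ideation hypotheses in Section 10A and the absence of a rule for intervals without a period. It does not depend on any one assumed share.

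The size does depend on assumptions. Break-even gains run from 14% to 33% over the shares shown. The detectable mediation effect rises from 0.11 to 0.13 to between 0.13 and 0.20 if 80% down to 40% of 624 people have a score. The statement in Section 10B that the study can detect any clinically significant mediation effect therefore does not carry over to this checklist.

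The primary and secondary efficacy analyses, and the treatment-utilization and belongingness measures, do not use this score and are unaffected.

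**What to change.** 1. Reconcile the instrument named in Table C1 with the checklist in Section 9 and Section 10A. State whether they are one measure or two, and whether the Table C1 measure can be answered without a suicidal period.
2. If it is confirmed to be separate and answerable by everyone, name it as the problem-solving mediator in both sections.
3. Otherwise, do not zero-score or impute the checklist. Define on the C-SSRS what counts as a suicidal period. Report the share with a period by arm at weeks 16, 34 and 52, then both subscales among those with a period, labelled descriptive and not a randomized comparison. Do not interpret the checklist as a mediator in the structural equation model.
4. In Section 10B, state that 0.11 to 0.13 assumes all 624 evaluable people have a mediator score and so does not apply to this checklist.

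Settle this before analysis by arm. Steps 1, 3 and 4 cost only wording. Step 2 does too if the Table C1 measure proves to be separate and suitable. The price is a weaker mechanism conclusion for one exploratory mediator.

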Standard Care. As is the case in most jails nationally, 23,34,35,178-180 Standard Care (SOC) for pretrial jail detainees at the study sites ( is screening (by an intake worker) and assessment of risk (by a social worker). Individuals considered to be at acute risk of suicide are placed on psychiatric observation in the jail, where they are stabilized to the extent possible during their jail detention (i.e., they may be high, manic, or floridly psychotic when detained and may only be in jail for a few days, often coming in on a Friday night and being released from court Monday). If jail staff determine a detainee's imminent suicide risk to decrease while they are in jail, they leave observation, enter the general jail population, and then are released with no community follow-up. If an individual on observation is released on bail, the jail will ask the person picking the detainee up to take him or her to the ED for evaluation; no further follow-up is provided. If an individual on observation goes to court, the jail provides a letter asking the court to have the person evaluated by a mental health professional before releasing him or her; no further follow-up is provided. Individuals identified by the jail as having a severe mental illness (i.e., schizophrenia, bipolar disorder) are provided with post-release appointments. Thus, research assessment and emergency referral for trial participants on the basis of suicidality should be considered "enhanced" care compared to current jail practice, in keeping with ethical obligations. We will also provide handouts with an overview of local community treatment and other relevant community resources (e.g., housing, food) to all study participants.

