Randomization and blinding. Randomization to SPI or SOC in a 1:1 ratio will occur in the jail after the baseline assessment; therefore, all baseline assessments will be "blind." Randomization will be stratified by jail, gender, and history of suicide attempts (yes or no). As in ongoing jail study, study counselors (who are available every day of recruitment; see Budget Justification) will meet with those assigned to the intervention condition within 24 hours of randomization. Typically, we recruit participants in the morning to meet with the interventionist's scheduled to come to the jail that afternoon or evening. Immediately after randomization, RAs will also review the study follow-up schedule, means of contacting the research staff, and participants' contacts with all participants. A different research assistant, who is blind to intervention assignment, will perform follow-up assessments. Information about a participants' experimental condition will be kept separately from the databases where research assistants will enter assessment data. Patients will be instructed at each visit that they are not to make any mention of their treatment condition while they are being interviewed by their assigned rater. At the beginning of each rating session, the rater will remind the patient that she/he is not to mention treatment condition during the interview with the rater.

The study statistician, will prepare the randomization schedule before the first participant is enrolled.

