Sample descriptors will include baseline demographics. Study inclusion criteria are based on suicide risk rather than diagnosis, but we will gather some basic diagnostic information (lifetime psychosis, mania/hypomania, and major depression) using MINI modules (see Table). We chose the MINI to keep assessment interviews to 1 hour: keeping participant burden minimal (and hence, study procedures feasible and enrollment and follow-up rates high) was our primary consideration. We will administer the MINI modules at 4 week post-release because: (1) we are assessing lifetime diagnosis, and (2) giving it at the 4 week follow-up best balances the length of all assessments.

Hospital and death records. Most of is covered by 2 large health systems. is covered by 3 systems. As in ED-SAFE (a 7-state, 8-site trial is covered by 3 systems. As in ED-SAFE (a 7-state, 8-site trial is covered by 3 systems. As in ED-SAFE, 8-site trial is covered by 3 systems. See C3), we will obtain releases of information from participants at study intake to conduct chart reviews at all of the hospital systems in each region. As in ED-SAFE, RAs will review charts

following a structured protocol, utilizing discharge codes, discharge summaries, medications, laboratory results, operation records, nursing notes, physician progress notes and other notes or comments to determine whether a suicide event occurred. ED-SAFE data showed that this approach is feasible and that it enhanced detection of suicide events over and above telephone follow-up assessment, uniquely identifying 43% of the 1871 detected suicide-related events. Thus, a combination of records review with phone assessment is a feasible and robust approach to detecting suicide-related events. We will also search the National Death Index for ICD-coded suicide deaths in our sample.

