directly to prison, not home), meaning that they are not actually eligible for the study, which is a study of suicide prevention in the year after release from pretrial jail detention. Therefore. individuals who go to prison directly from jail rather than back to the community will not be followed, and have been included in our study attrition estimates. This is a standard approach taken in other re-entry studies (e.g., R01 AA021732; U01 DA01619113) that must consent participants when their sentencing or release status is still unknown. Sentencing will occur independent of study condition, so their exclusion from analysis (no "at-risk" community months) will be unlikely to influence internal validity. We will follow all remaining participants who are released from jail to the community after the index incarceration through the 52-week postrelease period regardless of reincarceration, continued participation in SPI or SOC, or subsequent suicide attempts or hospitalizations. For randomized participants who are not released from jail by the assessment window closing date (see Section 10A), the study PIs can decide to terminate the participants, citing release from jail as a study requirement. If study termination was required, the affected individuals would be notified by study staff. Of the 92-94% of participants who are released from jail to the community after the index incarceration, we conservatively estimate that post-release follow-up rates will be 82% at 4 weeks, 80% at 16 weeks, 75% at 34 weeks and 70% at 52 weeks, with 85% of participants providing data for at least one post-release follow-up interview. Post-release follow-up rates in previous and ongoing studies have been higher than this. Therefore, we expect that 78% (85%) of the 92% who are released from iail) of the 800 enrolled participants will provide evaluable follow-up data. Count (e.g., suicide events) data from missed follow-ups will be gathered at later follow-ups when they occur, and we will collect medical record and death record data on all eligible (i.e., released) participants.

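### Restricting the MINI to the 4-week interview loses a diagnosis for about 22 participants who are interviewed later, and the plan does not say how the MINI modules define the severe-mental-illness moderator

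*Combined protocol and SAP*

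**What the plan says.** Section 9 treats diagnosis as a sample descriptor and gives two reasons for the timing. The first is "We will administer the MINI modules at 4 week post-release because: (1) we are assessing lifetime diagnosis"; the second is that week 4 best evens out interview length. In Table C1 the MINI is the only diagnostic instrument. It has no baseline mark, is limited to the 4-week visit, takes 10 minutes, and covers "lifetime psychosis, mania/hypomania, major depressive episode".

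Section 10A, under Predictors/Personalization, lists "severe mental illness (schizophrenia, bipolar disorder), substance use, and # of lifetime arrests as moderators", along with gender, race/ethnicity and suicide history, as variables to be explored. It gives no data source, scoring rule or handling rule for the severe-mental-illness variable.

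On timing, Section 4A states: "Randomization to SPI or SOC in a 1:1 ratio will occur in the jail after the baseline assessment". Under Sections 1H and 4A the in-jail SPI session and the first-week call are scheduled before week 4, and the 1-month call falls at about the same time.

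On follow-up, Section 10B states: "we conservatively estimate that post-release follow-up rates will be 82% at 4 weeks, 80% at 16 weeks". It adds that 85% of those released give at least one interview. Section 10A (Missing Data) lets later interviews recover self-reported counts and historical data, with weekly LIFE ratings as its example, and otherwise plans multiple imputation.

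**The concern.** The reason given for week 4 shows that the answer should not depend on when the question is asked. It gives no ground for refusing to ask at week 16, 34 or 52 when week 4 was missed. As written, someone who misses week 4 and is interviewed later has no MINI value, although study staff were speaking to that person.

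The moderator is also defined in terms the instrument does not use. Lifetime psychosis takes in more people than schizophrenia does. Mania/hypomania is a reasonable proxy for bipolar disorder, but the plan does not say that it will be used that way. Without a stated rule, the subgroup could be settled after the data are seen.

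This moderator has some particular interest, because standard care is not the same for everyone. Section 1H says: "Individuals identified by the jail as having a severe mental illness (i.e., schizophrenia, bipolar disorder) are provided with post-release appointments". Treatment utilization is also the plan's primary proposed mechanism. At stake is how complete and clear one exploratory moderator analysis will be.

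**Working it through.** **Inputs.** 800 enrolled; 92–94% released; among those released, 82% interviewed at week 4 and 85% interviewed at least once (all Section 10B); MINI at week 4 only (Table C1).

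**The plan's own figure.** Section 10B expects 78% "of the 800 enrolled participants will provide evaluable follow-up data". Check: 0.92 × 0.85 = 0.782, or 625.6 of 800. It reproduces.

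**The same chain applied to the MINI.**

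| Quantity | Formula | 92% released | 94% released |
|---|---|---|---|
| Released | 800 × release rate | 736 | 752 |
| At least one interview | released × 0.85 | 625.60 | 639.20 |
| Week-4 interview, so MINI | released × 0.82 | 603.52 | 616.64 |
| No MINI | released × 0.18 | 132.48 | 135.36 |
| No MINI, interviewed later | released × (0.85 − 0.82) | 22.08 | 22.56 |
| No MINI, never interviewed | released × 0.15 | 110.40 | 112.80 |

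The subtraction 0.85 − 0.82 is legitimate because anyone interviewed at week 4 is, by definition, among those with at least one interview. It requires only that both rates refer to released participants, as Section 10B presents them.

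**Share lost through the timing rule.** 22.08 / 625.60 = 3.5% of those interviewed at least once, and 3% of those released. Giving the MINI at the first completed interview would cut the unscored share of released participants from 18% to 15%.

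**Interview length.** In Table C1 the 16-, 34- and 52-week interviews carry the belongingness and coping measures (5 + 5 minutes), which week 4 does not. Week 52 also carries a 10-minute safety-plan interview. A moved MINI would therefore add 10 minutes to a visit that already has 10 or 20 minutes of items absent at week 4.

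**Definition.** Table C1 yields three module results: psychosis, mania/hypomania and major depressive episode. Section 10A needs one classification based on schizophrenia and bipolar disorder. No text connects the two.

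**The case against.** The plan has a fair defence. The timing is reasoned: the jail is a poor place for a diagnostic interview, and short interviews protect enrolment and retention. That stands, and nothing here asks for a baseline MINI. Section 10A plans multiple imputation, a comparison of missingness between arms, and a sensitivity analysis with extreme values. The catch-up provision for historical data might be read to include a lifetime diagnosis. However, Table C1 is explicit about week 4, so that reading is not secure and one sentence should settle it. The follow-up rates are labelled conservative, so the true losses may be smaller.

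A reader might infer more than the documents support:

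- *That the moderator can be scored only from the MINI.* Section 10A names no source. Jail and hospital records are also obtained, though for other stated purposes. The MINI is the only diagnostic instrument named, which is a weaker statement.
- *That a quarter of randomised participants are lost.* The product 1 − 0.92 × 0.82 = 24.6% (196 of 800; 22.9%, or 183, at 94% release) is correct arithmetic. It includes the 6–8% never released, whom the plan does not follow and excludes from analysis for every variable. The relevant figure is 18% of those released.
- *That a jail-recorded diagnosis should replace the MINI.* Section 1H describes a care practice. Nothing shows a diagnosis flag that is retrievable, dated before randomisation and comparable across the two jails. A person without a flag is not a confirmed negative, so the swap would exchange visible missingness for hidden misclassification.
- *That the subgroup will be selected differently by arm.* SPI contact before week 4 makes this possible, but the documents give no expected difference in response.

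**Conclusion.** The point holds as a minor improvement. The week-4 restriction costs about 22 diagnoses that later interviews could supply, and the plan's own reason for the timing does not require that loss. A further 110 or so released participants have no interview at all. Changing the visit does not help them, and they remain a matter for the planned imputation. The link between the MINI modules and the moderator is unstated, mainly on the schizophrenia side. The value is observed after randomisation, and only among responders, which a report of this subgroup should say.

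The sizes rest on the plan's projected rates of 92% release, 82% at week 4 and 85% ever interviewed. At 94% release the counts become about 135 without a MINI and 23 recoverable. The analysis is exploratory and the primary test does not depend on it.

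**What to change.** 1. In Table C1 and Section 9, have the MINI modules given at the first completed follow-up interview, which is week 4 if that interview is completed. The cost is about 10 extra minutes at one later interview for those who missed week 4. In Section 10A the windows for the later waves close after the 4-week window, so this is workable.
2. In Section 10A (Predictors/Personalization), name the MINI as the source and state which module results count as schizophrenia and which as bipolar disorder, or else rename the moderator to match what the modules measure. Fix this before any comparison by arm.
3. In the same place, note that the variable is collected after randomisation and only from participants who are interviewed.
4. If jail-record diagnoses prove retrievable and dated before randomisation, they may be used as a sensitivity definition alongside the MINI, but should not replace it.

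Items 2 and 3 cost a few sentences. Item 4 depends on what the jail records turn out to contain.
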